### 13.5.2. Exclusion Criteria for Sub-Study B

#### Phase 1b and Phase 2:

17. Documentation of any tumor-driving molecular alteration including but not limited to: BRAF, activating EGFR (mutations located in exons 18-21), ALK, ROS1, MET, RET. Testing for EGFR mutation is required if status is unknown.
18. Central lung lesion involving major blood vessels.
19. History of Grade  $\geq 2$  hemoptysis.
20. Gastrointestinal abnormalities including:
  - Inability to take oral medication.
  - Requirement for IV alimentation.
  - Prior surgical procedures affecting absorption, including total gastric resection.
  - Treatment for active peptic ulcer disease in the past 6 months.
  - Active GI bleeding as evidenced by clinically significant hematemesis, hematochezia or melena in the past 3 months without evidence of resolution by endoscopy or colonoscopy.
  - Malabsorption syndromes.
21. Requirement of anticoagulant therapy with oral vitamin K antagonists (see [Section 13.6.5.3](#) for allowed anticoagulant therapies).
22. Active bleeding disorder or other history of significant bleeding episodes within 30 days before first dose of study treatment.
23. History of aneurysm.
24. Evidence of inadequate wound healing.
25. Triplicate average baseline QTcF  $> 480$  msec.

#### Phase 1b only:

26. Concurrent or anticipated use of strong CYP3A4/5 inducers or strong CYP3A4 inhibitors within 14 days or 5 half-lives (whichever is longer) prior to Cycle 1 Day 1 and throughout the study. The topical use of these drugs is permitted (eg, 2% ketoconazole cream).

**Phase 2 only:**

27. Prior use of any anti-TIGIT mAb or anti-VEGF pathway therapy.
28. Concurrent or anticipated use of strong CYP3A4/5 inducers within 14 days or 5 half-lives (whichever is longer) prior to Cycle 1 Day 1 and throughout the study.

**Phase 2 Arms B1 and B2 (1st- Line) only:**

29. Prior treatment with anti-PD-1, anti-PD-L1, or anti-PD-L2 agents.

**Phase 2 Arm B3 (2nd/3rd - Line) only:**

30. Confirmed progressive disease on the first or second imaging tumor assessment after initiation of therapy for advanced/metastatic NSCLC.

**13.6. Study Intervention for Sub-Study B**

**Study Treatments:**

For purposes of this sub-study, study intervention refers to sasanlimab, axitinib, and SEA-TGT.

**Phase 1b Dose Levels:**

See [Table 25](#) and [Table 26](#) for dose scheme in the Doublet Cohorts and Triplet Cohorts, respectively. Participants will receive the following study treatments in each 21-day cycle:

- Sasanlimab SC, **CCI** (50 mg/mL, 2 mL per vial) on Day 1 of each cycle
- Axitinib:
  - 5 mg BID (1 × 5 mg oral tablet) (Doublet Cohorts Dose Level 0) or
  - 3 mg BID (3 × 1 mg oral tablet) (Doublet Cohorts Dose Level -1)
  - Triplet Cohorts Dose Level will be 1 of the 2 doses above based on dose finding.
  - Intra-patient dose increases up to 10 mg BID will be permitted according to guidelines in [Section 13.6.1.1](#).

- SEA-TGT IV (15 mg/mL, 150 mg/ vial) on Day 1 of each cycle:
  - 1 mg/kg (Triplet Cohorts Dose Level 0) or
  - 3 mg/kg (Triplet Cohorts Dose Level 1) or
  - 0.3 mg/kg (Triplet Cohorts Dose level -1)

**Phase 2 Dose Levels:**

RP2D of sasanlimab SC **CCI** + axitinib BID + SEA-TGT IV Q3W

**Table 27. Study Interventions: Sub-Study B (Sasanlimab + Axitinib + SEA-TGT)**

Intervention Name	Sasanlimab	Axitinib	SEA-TGT
Type	Biologic Product	Small Molecule Product	Biologic Product
Dose Formulation	Solution for injection	Tablet	Solution for IV infusion
Unit Dose Strength	50 mg/mL, 2 mL (100 mg total) vial	1 mg and 5 mg tablets	15 mg/mL (150 mg/vial)
Dosage Level(s)	CCI	3 mg and 5 mg BID	0.3, 1, or 3 mg/kg Q3W
Route of Administration	Subcutaneous	Oral	Intravenous
Use	Experimental	Experimental	Experimental
IMP or NIMP	IMP	IMP	IMP
Sourcing	Provided centrally by the sponsor	Provided centrally by the sponsor	Provided centrally by the sponsor
Packaging and Labeling	Study intervention will be provided in vials. Each vial will be labeled as required per country requirement.	Study intervention will be provided in high-density polyethylene bottles. Each bottle will be labeled as required per country requirement.	Study intervention will be provided in vials. Each vial will be labeled as required per country requirement.
Former Names or Aliases	PF-06801591 RN888	Inlyta® AG-013736	SGN-TGT

**13.6.1. Administration of Sub-Study B Investigational Products**

Sasanlimab should be administered first, followed by axitinib, and then SEA-TGT, when possible and in accordance with axitinib BID schedule.

Refer to [Section 6.1.1](#) for details about the administration of sasanlimab, and below for details about administration of the other Sub-Study B products.

**13.6.1.1. Administration of Axitinib**

Axitinib will be swallowed whole with a glass of water and with or without food. Axitinib should be taken 12 ± 2 hours apart in the morning and in the evening at approximately the

same times every day. If a participant vomits at any time after dosing, the dose should not be re-administered, and the participant should take the next scheduled dose. Any missed dose may be taken up to 3 hours before the next scheduled dose, otherwise it should be skipped. Doses that are omitted for AEs should not be made up during the day, or at the end of the dosing period. Additional information regarding axitinib administration is provided in the IP Manual.

Axitinib will begin on Cycle 1 Day 1 and will be self-administered at home twice per day continuously, except on study visit days, when it should be administered at the study site.

Axitinib intra-patient dose increase is permitted in Phase 1b and Phase 2 after completing 16 weeks of axitinib treatment for participants who tolerate the current axitinib dose with no Grade  $\geq 2$  drug-related adverse events for 2 consecutive weeks, and have blood pressure  $\leq 150/90$  mm Hg, and are not receiving antihypertensive medication. These participants will have the option to have their axitinib dose increased by one dose level in subsequent cycles, up to a maximum dose of 10 mg BID; the available doses are 3 mg BID, 5 mg BID, 7 mg BID, and 10 mg BID. Particular attention should be provided to a patient's overall safety profile prior to implementing intra-patient dose increase for axitinib.

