**Figure 3. Sub-Study B Design**

### 13.4.1. Phase 1b Design

Phase 1b will enroll participants in any line therapy for advanced NSCLC with no restrictions on the types of previous therapies, and who have any PD-L1 expression status. First, the safety of the sasanlimab and axitinib combination will be confirmed. Up to 2 dose levels of axitinib given in combination with sasanlimab CCI will be investigated (Table 25). The decision to de-escalate (from 5 mg BID to 3 mg BID) will be based on mTPI decision criteria based on the number of DLT evaluable patients and number of DLTs in those participants.

Initially 3-4 participants will be treated with sasanlimab CCI axitinib 5 mg BID and monitored during the 21-day DLT evaluation period (Cycle 1). If the mTPI decision criteria allows escalation, then the triplet cohort may be opened. Otherwise, the doublet cohort can be expanded with an additional 3 patients enrolled or de-escalated to the lower dose (3 mg BID) per the mTPI decision criteria.

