**Table 26. Sub-Study B, Phase 1b, Triplet Cohorts Dose Levels**

Dose Level	Sasanlimab	Axitinib*	SEA-TGT
1	CCI	3 or 5 mg BID	3 mg/kg IV Q3W
0 (Starting Dose)	CCI	3 or 5 mg BID	1 mg/kg IV Q3W
-1	CCI	3 or 5 mg BID	0.3 mg/kg IV Q3W

DLT period = 1 cycle of 21 days.  
 mTPI dose finding schema will be used for dose finding.  
 \*Axitinib dose will be determined by the doublet cohorts and will be fixed in the triplet cohorts.

A minimum of 3 DLT-evaluable participants will be required in each cohort; additional participants will be enrolled in the specific enrollment cohort to replace participants who are not considered DLT-evaluable, where required. When all DLT-evaluable participants treated in a given enrollment cohort have completed the DLT observation period or experienced a DLT, whichever occurs first, the posterior probabilities for the risk of DLT for new

participants at different dose levels for the combination of interest will be evaluated. If the toxicity rate of the currently used dose level is far smaller than the target probability of toxicity (pT) of 0.30, the mTPI will recommend escalating the dose level; if it is close to pT, the mTPI will recommend continuing at the current dose; if it is far greater than pT, the mTPI will recommend de-escalating the dose level. The mTPI dose de-escalation/escalation recommendation will be based on the estimated toxicity rate and 3 intervals (underdosing, target toxicity, and excessive toxicity) as shown below:

- If current dose is in the underdosing [0, 0.25) toxicity interval: escalate to next higher dose;
- If current dose is in the target toxicity [0.25, 0.35) toxicity interval: stay at current dose;
- If current dose is in the excessive toxicity or overdosing [0.35, 1] toxicity interval: de-escalate to a lower dose

Refer to [Section 13.9](#) and [Section 13.10.6](#) for more details on the mTPI design and decision rules.

The number of participants to be enrolled in Phase 1b will depend upon the observed safety profile, which will determine the number of participants at each dose level and the number of dose levels explored.

It is anticipated that up to approximately 20 total participants will be enrolled in Phase 1b starting with Dose Level 0 of the doublet cohorts, and including the triplet cohorts.

An RP2D below the MTD, or highest safe dose tested, may be determined based on other safety, clinical activity, PK, and pharmacodynamic data.

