#### **13.4.6. Maximum Tolerated Dose**

The MTD is the highest studied dose level associated with a DLT rate of <35% among the participants treated at that dose level following the mTPI method.

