#### **13.6.1.2. Administration of SEA-TGT**

SEA-TGT will be administered on Day 1 of every 21-day cycle by IV infusion. SEA-TGT must not be administered as an IV push or bolus.

Weight-based dosing is based on the participant's actual body weight and weight must be measured at each visit per the [SoA](#). Doses must be adjusted for participants who experience a  $\geq 10\%$  change in weight compared to the body weight used to calculate the initial dose. Other dose adjustments for changes in body weight are permitted per institutional standard. Rounding is permissible within 5% of the nominal dose.

Infusion duration will vary depending on the method of infusion administration and the dose. Refer to the IP Manual for further details. SEA-TGT will be administered via stepwise infusion. In a stepwise infusion, the infusion rate is increased at set time intervals until a defined maximum rate of infusion is reached. As clinical experience with stepwise infusion of SEA-TGT evolves, the maximum rate and/or the infusion rate may change (ie, increase or decrease); the method of administration may also change. The IP Manual will specify any such changes.

Participants will be observed for at least 2 hours post-dose on Cycles 1, 2, and 3.

If a participant does not tolerate the infusion, the infusion duration for that participant may be increased; the infusion duration in subsequent infusions may also be increased per investigator discretion with medical monitor/sponsor approval. Conversely, if a participant tolerates consecutive infusions without IRR Grade  $>1$ , the infusion duration may be shortened (ie, administered at a faster rate) at the discretion of the investigator following consultation with the medical monitor/sponsor, the implementation of which may be dose-

cohort specific. For additional information regarding management of IRRs, see [Section 13.6.6.1.1](#).

Pre-medication is not required. However, subjects who experience IRRs may receive subsequent treatment with premedication as indicated in [Section 13.10.4](#). In such cases, premedication should be administered at least 30 minutes prior to the infusion and includes antihistamines (eg, diphenhydramine 50 mg IV or equivalent); famotidine 40 mg IV or equivalent, corticosteroids (e.g., hydrocortisone 100 mg IV or equivalent), or antipyretics, such as acetaminophen/paracetamol (eg, 500 to 1,000 mg oral dose).

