**Table 30. Dose Finding Rules**

		Number of Participants Treated at Current Dose															
r/n		3	4	5	6	7	8	9	10	11	12	13	14	15	16	17	18
Number of DLTs	0	E	E	E	E	E	E	E	E	E	E	E	E	E	E	E	E
	1	S	S	S	E	E	E	E	E	E	E	E	E	E	E	E	E
	2	D	S	S	S	S	S	S	S	E	E	E	E	E	E	E	E
	3	DU	DU	D	S	S	S	S	S	S	S	S	S	S	S	E	E
	4		DU	DU	DU	D	D	S	S	S	S	S	S	S	S	S	S
	5			DU	DU	DU	DU	DU	D	S	S	S	S	S	S	S	S
	6				DU	DU	DU	DU	DU	DU	D	S	S	S	S	S	S
	7					DU	DU	DU	DU	DU	DU	DU	D	S	S	S	S
	8						DU	DU	DU	DU	DU	DU	DU	DU	DU	D	S
	9							DU	DU	DU	DU	DU	DU	DU	DU	DU	DU
	10								DU	DU	DU	DU	DU	DU	DU	DU	DU
	11									DU	DU	DU	DU	DU	DU	DU	DU
	12										DU	DU	DU	DU	DU	DU	DU
	13											DU	DU	DU	DU	DU	DU
	14												DU	DU	DU	DU	DU
	15													DU	DU	DU	DU
	16														DU	DU	DU
	17															DU	DU
18																DU	

**E** = Escalate to the next higher dose level  
**S** = Stay at the current dose level  
**D** = De-escalate to the next lower dose level  
**DU** = The current dose level is unacceptably toxic and should be eliminated from further dose finding  
**DLTs** = Dose Limiting Toxicities; Targeted DLT rate=30%

Select escalation/de-escalation algorithms for total number of participants treated at the current dose level (current and previous cohorts):

With 3 participants treated at current dose level

- 0 DLT: escalate
- 1 DLT: remain at the same dose
- 2 DLTs: de-escalate
- 3 DLTs: de-escalate and consider current dose as intolerable

With 6 participants treated at current dose level

- 0-1 DLT: escalate
- 2-3 DLTs: remain at the same dose
- 4-6 DLTs: de-escalate and consider current dose as intolerable

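### Sub-Study B's individual titration rule lets a participant move from axitinib 3 mg BID up to 5 mg BID even if mTPI dose finding has rejected 5 mg BID

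*Protocol*

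**What the plan says.** Section 13.6.1.1 (Administration of Axitinib): "Axitinib intra-patient dose increase is permitted in Phase 1b and Phase 2 after completing 16 weeks of axitinib treatment". To qualify, a participant must have gone two weeks running at the current dose without a drug-related event of Grade 2 or higher, have blood pressure no higher than 150/90 mm Hg, and take no antihypertensive. The increase is one level at a time on a ladder of 3, 5, 7 and 10 mg BID. The remaining safeguard is a general caution: "Particular attention should be provided to a patient's overall safety profile prior to implementing intra-patient dose increase for axitinib". Section 13.6 (Phase 1b Dose Levels) repeats the permission: "Intra-patient dose increases up to 10 mg BID will be permitted".

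The axitinib dose for the combination comes from dose finding. Section 13.4.1: "The decision to de-escalate (from 5 mg BID to 3 mg BID) will be based on mTPI decision criteria". Table 26, footnote: "Axitinib dose will be determined by the doublet cohorts". Table 30 defines DU as: "The current dose level is unacceptably toxic and should be eliminated from further dose finding". Section 13.4.6: "The MTD is the highest studied dose level associated with a DLT rate of <35" percent.

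**The concern.** The doublet cohorts exist to decide whether 5 mg BID is acceptable with sasanlimab. Apart from a choice made on other data, 3 mg BID becomes the cohort dose because mTPI told the study to leave 5 mg BID. In that case the first rung of the titration ladder is the dose just rejected. The individual conditions show tolerance of 3 mg BID only, and the 5 mg BID dose would now be given in a triplet whose safety profile Section 13.2.3 says is not yet characterised.

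The protocol uses firmer controls elsewhere. Section 13.6.1.2 allows a SEA-TGT infusion to be shortened only "at the discretion of the investigator following consultation with the medical monitor/sponsor", and Section 12.6.6.2 lists toxicities after which encorafenib or binimetinib may not be re-escalated. No such control covers a return to a rejected axitinib dose.

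**Working it through.** **1. Does any text bar the step?**

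| Provision | Effect on a step from 3 to 5 mg BID after 5 mg BID is rated D or DU |
|---|---|
| 13.6.1.1 and 13.6 | Permit it on individual conditions; no link to mTPI, MTD or RP2D |
| Table 30, DU | Removes the level from dose finding only |
| 4.3.5 and Phase 2 Dose Levels | Define the cohort's dose; silent on later titration |
| 13.4.1, cumulative DLT review in Phase 2 | Does not automatically reach a week-16 increase: the DLT window is days 1 to 21 (13.4.5), and a later event counts only after sponsor-investigator consultation (4.3.3, criterion 11) |
| 13.8.2.1, 13.10.5, 9.6 | Home blood pressure checks, withhold/reduce rules and ongoing AE review; none bars the step |

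Later steps to 7 or 10 mg BID do require that the participant has tolerated 5 mg BID. The gap examined here is the first step.

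**2. Reproducing Table 30.** Inputs from Section 13.10.6: target 0.30, e1 = e2 = 0.05. Assumed: a Beta(1,1) prior, and elimination when P(rate > 0.30) exceeds 0.95. The decision goes to the interval with the largest posterior mass divided by interval length.

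Example, 2 DLTs in 3: the posterior is Beta(3,2), with distribution function 4x³ − 3x⁴.
- [0, 0.25): 0.051/0.25 = 0.20
- [0.25, 0.35): (0.126 − 0.051)/0.10 = 0.76
- [0.35, 1]: 0.874/0.65 = 1.34, the largest
- P(rate > 0.30) = 0.916, below 0.95, so the rating is D, as printed

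Of 139 cells checked, 138 agree, including every cell for n = 3 to 10. The exception (3/16, printed S, computed E) is irrelevant here.

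**3. What a rejection implies.** The lowest observed rate in any D or DU cell is 8/17 = 47%, against the 35% MTD limit. Posterior P(rate > 0.35):
- D: 2/3, 0.874; 4/7, 0.894
- DU: 4/6, 0.944; 3/4, 0.946; 5/7, 0.975; 3/3, 0.985

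**4. How often 3 mg BID is selected with 5 mg BID left rejected.** Exact binomial enumeration of Table 30 as printed. Assumed: one expansion by 3 at each dose; true rate p at 5 mg BID and p/2 at 3 mg BID; cases where 3 mg BID is itself rated D or DU are excluded.

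Worked case, p = 0.30, first cohort of 3:
- 2/3 (D): 3 × 0.09 × 0.7 = 0.189
- 3/3 (DU): 0.027
- 1/3, then 3/3 in the expansion (4/6, DU): 0.441 × 0.027 = 0.012
- First rating D or DU: 0.189 + 0.027 + 0.012 = 0.228, of which DU 0.039
- 3 mg BID at 0.15 is rated D or DU: 0.061 + 0.001 = 0.062, so it passes with 0.938
- Not re-tested: 0.228 × 0.938 = **0.214**
- Re-tested with 3 more whenever 5 mg BID was D and 3 mg BID is rated E (probability 0.814). It ends at 4/6 or 5/6 (DU) with probability 0.216: 0.189 × 0.814 × 0.216 = 0.033. 3 mg BID rated S, so 5 mg BID stays D: 0.189 × (0.938 − 0.814) = 0.023. DU at the first rating: 0.039 × 0.938 = 0.037. Total **0.093**

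All cases (DU alone in brackets):

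| Design path | p = 0.20 | p = 0.30 | p = 0.40 |
|---|---|---|---|
| First cohort 3, re-tested | 0.03 (0.02) | 0.09 (0.07) | 0.21 (0.15) |
| First cohort 4, re-tested | 0.04 (0.03) | 0.13 (0.10) | 0.29 (0.22) |
| First cohort 3, not re-tested | 0.10 (0.01) | 0.21 (0.04) | 0.34 (0.08) |
| First cohort 4, not re-tested | 0.05 (0.03) | 0.15 (0.09) | 0.31 (0.19) |

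Setting the 3 mg BID rate anywhere from one third to two thirds of the 5 mg BID rate moves any total by at most 0.03.

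**The case against.** The two rules answer different questions. mTPI estimates the Cycle 1 DLT rate in unselected participants who start at 5 mg BID. Titration concerns someone who has already had 16 weeks on axitinib and meets tolerance conditions, so the cohort rate does not carry over directly. Axitinib is marketed and 5 mg BID is its approved dose (13.4.4.1), whereas SEA-TGT is still in its first-in-human study, so tighter control of SEA-TGT is reasonable. The step is one level and quickly reversible: Section 13.10.5 gives a half-life of 2 to 4 hours. Several events must also coincide, and at a true rate of 0.20 a rejection would be a false alarm.

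The 35% comparison is also weaker than it looks. Table 30 rates 2/4 and 3/6 as S, and both are 50%, so an observed rate above 35% does not by itself separate rejected from retained levels.

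All of this is fair, and it limits the size of the point. The argument should rest on the D or DU rating, not on the observed rate. The objections also support a softer rule for D. None of them supplies a bar, and selection for tolerance of 3 mg BID is weak reassurance about a level the study has eliminated.

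**Conclusion.** The concern holds. Followed as written, the protocol allows participants to be raised to a dose that its own dose finding has eliminated, on individual conditions and without sponsor agreement. The problem arises only if 5 mg BID is rejected and 3 mg BID is carried forward. Under the assumed rates the chance of that is 0.03 to 0.10 at a true DLT rate of 0.20, 0.09 to 0.21 at 0.30, and 0.21 to 0.34 at 0.40. These figures depend on the assumed rates, cohort sizes and re-test policy. They are upper bounds on exposure, and no exposure probability can be computed from the document. No endpoint, analysis or sample size is affected. It is a participant-safety gap that should be fixed because the remedy is so cheap.

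**What to change.** Add to Section 13.6.1.1:

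> No participant may be increased to or beyond an axitinib dose level eliminated (DU) in dose finding. An increase to or beyond a level whose final rating is D requires prior agreement of the medical monitor/sponsor, taking into account which study drug the DLTs were attributed to.

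The softer rule for D reflects that under Section 4.3.3 a DLT may be attributed to any drug in the combination, and that 5 mg BID is the approved axitinib dose. The rest of the titration policy stands.

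The cost is two sentences in an amendment. If 5 mg BID is rejected, fewer participants can be increased (DU), or one consultation is needed first (D). If it is not rejected, nothing changes.

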#### **13.6.1.2. Administration of SEA-TGT**

SEA-TGT will be administered on Day 1 of every 21-day cycle by IV infusion. SEA-TGT must not be administered as an IV push or bolus.

Weight-based dosing is based on the participant's actual body weight and weight must be measured at each visit per the [SoA](#). Doses must be adjusted for participants who experience a  $\geq 10\%$  change in weight compared to the body weight used to calculate the initial dose. Other dose adjustments for changes in body weight are permitted per institutional standard. Rounding is permissible within 5% of the nominal dose.

Infusion duration will vary depending on the method of infusion administration and the dose. Refer to the IP Manual for further details. SEA-TGT will be administered via stepwise infusion. In a stepwise infusion, the infusion rate is increased at set time intervals until a defined maximum rate of infusion is reached. As clinical experience with stepwise infusion of SEA-TGT evolves, the maximum rate and/or the infusion rate may change (ie, increase or decrease); the method of administration may also change. The IP Manual will specify any such changes.

Participants will be observed for at least 2 hours post-dose on Cycles 1, 2, and 3.

If a participant does not tolerate the infusion, the infusion duration for that participant may be increased; the infusion duration in subsequent infusions may also be increased per investigator discretion with medical monitor/sponsor approval. Conversely, if a participant tolerates consecutive infusions without IRR Grade  $>1$ , the infusion duration may be shortened (ie, administered at a faster rate) at the discretion of the investigator following consultation with the medical monitor/sponsor, the implementation of which may be dose-

cohort specific. For additional information regarding management of IRRs, see [Section 13.6.6.1.1](#).

Pre-medication is not required. However, subjects who experience IRRs may receive subsequent treatment with premedication as indicated in [Section 13.10.4](#). In such cases, premedication should be administered at least 30 minutes prior to the infusion and includes antihistamines (eg, diphenhydramine 50 mg IV or equivalent); famotidine 40 mg IV or equivalent, corticosteroids (e.g., hydrocortisone 100 mg IV or equivalent), or antipyretics, such as acetaminophen/paracetamol (eg, 500 to 1,000 mg oral dose).

Please refer to the IP manual for further instructions on the administration of SEA-TGT.

